PIS	Patient information sheet
PLCO	Prostate, lung, colorectal and ovarian study
QoL	Quality of life
RCTs	Randomised controlled trials

UCSD-SBQ University of California San Diego Shortness of Breath Questionnaire

VAS Visual Analogue Scale

1 Background

1.1 Interstitial Lung Disease

Interstitial lung disease (ILD) represents a heterogeneous group of diseases of either known or unknown aetiology with different pathogenesis and prognosis. Idiopathic pulmonary fibrosis (IPF) is a chronic progressive fibrotic lung disease and the most common form of ILD. It is characterised by an irreversible loss of lung function with the development of debilitating breathlessness that ultimately leads to death. The prognosis of IPF is worse than most cancers with an average life expectancy of three to five years ¹. For decades immunosuppression with a combination of corticosteroids and azathioprine was the standard treatment; however it was subsequently shown that this regimen was actually associated with increased mortality ². Until recently there has been a dearth of evidence-based treatment options available for managing IPF. Over the last 5 years, disease modifying anti-fibrotic agents have been developed which have been shown to slow the progression of the disease ^{3,4}. As a consequence, earlier diagnosis through a specialist multidisciplinary team (MDT) has become an essential step in the management of ILD ⁵. However, patients with IPF often report significant delays before receiving the correct diagnosis ⁶. The British Thoracic Society (BTS) IPF registry demonstrates that patients often have symptoms for over 12 months and have a significant disease burden before presenting to a specialist ⁷. With the availability of disease modifying management strategies it is important to identify patients early in their disease course to have maximal impact on the natural progression of ILDs specifically IPF. Lung cancer screening strategies provide a unique opportunity to identify patients with previously undiagnosed ILDs.

1.2 Lung Cancer

Lung cancer is the world's leading cause of cancer-related death (1.6 million deaths/year) ⁸. The main risk factor is smoking ⁹. Prevention through smoking cessation is paramount ¹⁰⁻¹², however unaided quit rates are <5% at 12 months ¹³. There are 9 million smokers in England ¹³, smoking-related morbidity and mortality will remain a major public health burden for many years to come ¹⁴. In the UK, 45,500 people are diagnosed with lung cancer each year. Most patients (\approx 70%) present with advanced incurable disease, often as an emergency ¹⁵. Survival is poor (1-yr 32%, 5-yr 9.5%) ^{16,17} and lower than other equivalent nations ^{18,19}. Manchester has the highest rate of premature death in the country and lung cancer is the leading cause, responsible for more deaths than all other cancers combined ²⁰. Detection and radical treatment of early stage disease is associated with long-term survival. However, early stage lung cancer is often clinically silent or associated with non-specific symptoms, therefore the window for curative treatment is frequently lost. More effective diagnosis of symptomatic lung cancer through awareness campaigns, e.g. 'Be Clear on Cancer', is valuable but this approach alone is unlikely to transform outcomes, as symptoms are most commonly associated with advanced disease ²¹.

1.3 Low dose CT screening for lung cancer

Numerous observational²²⁻²⁴ and randomised controlled trials (RCTs)²⁵⁻³⁰, in asymptomatic at risk populations, have demonstrated the efficacy of low dose computed tomography (LDCT) to detect early stage non-small cell lung cancer (NSCLC), the most common pathological subtype ($\approx 88\%$). The largest study, the National Lung Screening Trial (NLST, n=53,454), demonstrated a reduction in lung cancer specific (20%) and overall mortality (6.7%) with annual LDCT screening compared to chest x-ray (CXR)²⁶. The US Preventative Services Task Force now recommends individuals aged 55-80 with a smoking exposure compatible with NLST be offered annual LDCT screening³¹. Recently, the UK Lung Cancer Screening Pilot (UKLS) confirmed the benefit of screening high-risk smokers with LDCT in a UK setting²⁸. Most cancers detected were early stage (85.7%, n=36/42) and 83.3% underwent surgical resection (national resection rate 16%)³². Estimated cost effectiveness was £8,466 per quality adjusted life year (QALY)²⁸, well below the NICE threshold for UK implementation (£20-30,000/QALY). Mortality data from the European NELSON randomised trial (n=15,822) is awaited²⁵. Several important issues that remain unresolved include optimisation of identification of high-risk individuals for screening, embedding smoking-cessation in screening programmes, ensuring participation in 'hard to reach' at-risk populations^{33,34}, and understanding how best to deal with additional non-lung cancer findings.

1.3.1 Optimising screening participation

Current smoking and lower socio-economic status (SES) were associated with reduced participation in UKLS³⁵, this participation bias has been reported in other RCTs^{36,37} and inequalities in uptake according to SES is common to other screening programmes^{38,39}. Several studies report differences in attitudes to screening between current and never smokers⁴⁰⁻⁴²; how best to identify and engage this 'hard-to-reach' population remains a critical issue⁴³⁻⁴⁵ and a priority area for implementation^{46,47}. Travel was the most common reason for non-participation in UKLS⁴⁸, therefore the Manchester Early Detection of Lung Disease Pilot used a mobile CT scanner located in convenient community settings to improve accessibility, an approach that has been effective in breast cancer screening⁴⁹.

1.3.2 Defining the threshold for screening

Retrospective analysis of NLST, after stratification according to lung cancer risk, demonstrated that the majority of cancers (88%) were detected in the three highest risk quintiles and only 1% in the lowest⁵⁰. The number needed to screen (NNS) to save 1 life was 161 in the highest risk group and 5,276 in the lowest; higher lung cancer risk was also associated with lower screening-related harms⁵¹. The more precise selection of higher risk smokers may improve screening efficacy, but the optimal method to select participants is unclear. In UKLS, screening was offered if 5-year lung cancer risk was $\geq 5\%$, as calculated by the Liverpool Lung Project model (LLP_{v2})⁵². Another model (PLCO_{m2012}), developed using the much larger Prostate, Lung, Colorectal,

Ovarian RCT (PLCO, n= 154,901)⁵³, performed significantly better than NLST selection criteria (sensitivity 83% vs. 71%) and 41.3% fewer cancers were missed⁵⁴. Further analysis indicated that the mortality benefit of LDCT screening was evident only above a 6-year lung cancer risk threshold of 1.5% when NNS to prevent one LC death was lower than NLST (NNS: PLCO 255 vs. NLST 320)⁵⁵.

1.4 ILD and lung cancer screening

Several common features in the pathogenesis of ILD and lung cancer have been determined. There is evidence to suggest an association between various forms of ILD and lung cancer⁵⁶. Several studies have published data on the prevalence of interstitial lung disease in patients undergoing low-dose CT for lung cancer screening. A trial at Mayo Clinic in current and former smokers identified “diffuse lung disease” in 9 (0.9%) of 1,049 participants²². An Irish trial identified idiopathic pulmonary fibrosis in 6 (1.3%) of 449 current smokers who underwent low-dose CT screening for lung cancer⁵⁷. Sverzellati et al evaluated 692 participants in the Multicentric Italian Lung Detection CT screening study and reported a respiratory bronchiolitis pattern in 109 (15.7%), a usual interstitial pneumonia pattern in 2 (0.3%), and other patterns of chronic interstitial pneumonia in 26 (3.8%)⁵⁸. The National Lung Screening Trial reported that the frequency of “clinically significant” incidental findings (including pulmonary fibrosis) in all participants was 7.5%. A retrospective analysis of 884 participants at a single site in this trial identified interstitial lung abnormalities (ILA) in 86 participants (9.7%)⁵⁹. These abnormalities were further categorized as nonfibrotic in 52 (5.9%) of 884, fibrotic in 19 (2.1%) of 884, and mixed fibrotic and nonfibrotic in 15 (1.7%) of 884. Follow-up CT at 2 years in this trial demonstrated improvement in 50% and progression in 11% of patients who had nonfibrotic abnormalities, while fibrotic abnormalities improved in no cases and progressed in 37%. Interstitial lung abnormalities were more common in those who currently smoked and in those with more pack-years of cigarette smoking. These trials suggest that low-dose CT screening for lung cancer can detect the most common forms of interstitial lung disease in this at-risk population which is important for prognosis and subsequent management. Interstitial lung abnormalities progression on CT has been shown to be associated with increased rate of pulmonary function decline and increased mortality⁶⁰. No direct comparison has been made between ILD patients diagnosed through a screening programme and those diagnosed through a ‘standard’ non-screening pathway and the impact this may have on long term outcomes.

2 Rational for study

A number of lung cancer screening programmes are underway in the UK with the aim of establishing a national screening programme in the future. As well as identifying early stage lung cancer, these programmes also provide a unique opportunity to diagnose other prevalent respiratory diseases, including ILD, at an early asymptomatic stage. Early detection of ILD through these programmes provides an opportunity to diagnose and establish treatment early and potentially have a significant impact on disease progression and symptomatic burden.

3 Aims and Objectives

3.1 Objectives

3.1.1 Primary Objectives

To determine the prevalence of ILD in a community-based lung cancer screening programme.

3.1.2 Secondary Objectives

To compare patients diagnosed with ILD in a lung cancer screening programme to those diagnosed through routine care, assessing a number of parameters:

1. Quality of life, symptoms and psychological burden at diagnosis.
2. MDT agreed type and radiological pattern of disease as depicted by ATS/ERS ILD criteria⁶¹.
3. Lung function (Forced vital capacity (FVC) and transfer factor (DLCO) at diagnosis.
4. Treatment strategies

3.2 Outcome Measures

3.2.1 Primary Measures

The prevalence and incidence of ILD in participants of a community-based lung cancer screening programme.

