4.1 Inclusion criteria

- Age 50-80
- Ever-smokers (current or previous)
- MDT diagnosis of ILD detected through lung cancer screening or through a non-screening pathway
- Attending the regional ILD clinic

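### Does naming incidence beside prevalence in the primary measure, without a stated case criterion or denominator, leave the primary result open?

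*Combined protocol and SAP*

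**What the plan says.** Section 3.1.1 gives the primary objective as "To determine the prevalence of ILD in a community-based lung cancer screening programme". Section 3.2.1 gives the primary measure as "The prevalence and incidence of ILD in participants of a community-based lung cancer screening programme". Neither defines a case. Section 6 says that clinical and demographic analyses are descriptive; it gives no estimator or interval for either quantity.

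The material for both quantities is in section 5. Under the screening service, people above the lung cancer risk threshold were offered a programme (the text attaches n=1,450) with a low-dose CT at baseline and another 12 months later, in 2016 and 2017. Under the ILD MDT, any ILA on a scan was referred to the MDT. Those the MDT thought had changes suggesting significant ILD went on to the regional clinic. The entry criterion for the clinic study, in section 4.1, is "MDT diagnosis of ILD detected through lung cancer screening or through a non-screening pathway".

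Section 1.4 reviews other screening cohorts. It opens with "Several studies have published data on the prevalence of interstitial lung disease in patients undergoing low-dose CT for lung cancer screening" and then gives results under several labels, among them diffuse lung disease in "9 (0.9%) of 1,049 participants". In one cohort of 884, ILA was found in 86 (9.7%), divided as "nonfibrotic in 52 (5.9%) of 884, fibrotic in 19 (2.1%) of 884, and mixed fibrotic and nonfibrotic in 15 (1.7%) of 884".

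**The concern.** An objective and its measure should name the same quantity, and here the measure has an extra one. Incidence also needs more than prevalence does: a group free of disease at the start, a second look at that group, and a rule for what counts as new. The primary measure supplies none of these. People enrolled at the clinic cannot supply them either, since each already has a diagnosis.

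The documents also mention several levels of abnormality: ILA on the scan report, the MDT's judgement of significance, and an MDT diagnosis. If the primary result could be computed at any of these levels, the same scans could give quite different answers. Someone flagged at round 1 but judged not significant, then judged significant at round 2, would be a prevalent case at the widest level and an incident case at a narrower one. Both rounds are already past, so the level could in principle be chosen after the counts were seen. The figure 1,450 might also mean people offered the programme or people scanned.

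**Working it through.** The plan states no target precision, sample size or event count for the primary measure, so there is no design figure to reproduce.

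**1. Whose data.** Section 3.2.1 refers to participants of the screening programme, not to clinic enrollees. Enrollees all have ILD, so they could supply neither prevalence nor incidence; that difficulty is not special to incidence. The programme's two rounds can supply both.

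**2. Which case.** Sections 3.1.1 and 3.2.1 both say ILD; neither says ILA. Section 3.1.2 (item 2) refers to the MDT-agreed type of disease, section 3.2.2 takes diagnosis from MDT proformas, and section 4.1 requires an MDT diagnosis. In section 5, ILA is what triggers referral to the MDT. These are successive steps on one pathway rather than competing definitions.

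**3. The resulting estimators.**
- Prevalence = MDT-diagnosed ILD at round 1 ÷ people with a baseline scan.
- New cases at 12 months = first MDT diagnosis at round 2 ÷ people rescanned who were not cases at round 1.

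If a round-1 judgement of not significant means that no ILD diagnosis was made, the person in the example above is a non-case at round 1 and a new case at round 2.

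**4. The apparent effect of the case level.** Inputs are the 884-person cohort in section 1.4 and the 1,450 in section 5, with everyone assumed scanned. Intervals are exact (Clopper-Pearson) 95%.

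| Level | Proportion | × 1,450 | 95% CI |
|---|---|---|---|
| Any ILA | 86/884 = 9.73% | 141 | 8.25–11.37% |
| Any fibrotic component | (19 + 15)/884 = 3.85% | 56 | 2.93–4.99% |
| Fibrotic only | 19/884 = 2.15% | 31 | 1.46–3.02% |

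The ratios are 86/34 = 2.5 and 86/19 = 4.5. With 1,000 scanned, the first two intervals become 7.94–11.70% (97 cases) and 2.70–5.18% (38 cases), so the meaning of 1,450 does not create the contrast.

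The arithmetic is right, but the inference fails. Since 52 + 19 + 15 = 86, the smaller groups are parts of the larger one. A subset is smaller by construction, and non-overlapping intervals between nested counts add nothing. No section equates MDT-diagnosed or significant ILD with fibrotic change, and none names any ILA as the outcome.

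**5. The apparent effect on incidence.** Section 1.4 reports "Follow-up CT at 2 years in this trial demonstrated improvement in 50% and progression in 11% of patients who had nonfibrotic abnormalities".
- Nonfibrotic ILA carried over: 1,450 × 52/884 = 85.3 people.
- Progressing in two years: 85.3 × 0.11 = 9.4.
- Progressing in 12 months at a constant rate: 1 − √0.89 = 5.66%, so 85.3 × 0.0566 = 4.8.
- At risk if any fibrotic component counts as disease: 1,450 − 55.8 = 1,394, all assumed rescanned.
- Proportion: 4.8/1,394 = 0.35%. It is 0% if none cross the line and 9.4/1,394 = 0.67% if all two-year progression falls in the first year.

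The base is thin: 11% of 52 is 5.7 people. Taking 6/52, the exact 95% interval is 4.35–23.44%, or about 4 to 20 two-year progressors among the 85. The calculation also assumes that radiological progression means becoming a case. On the MDT reading, any of these people first diagnosed at round 2 are simply counted as new.

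**6. What striking out incidence would do.** The prevalence numerator and denominator are untouched. The round-2 quantity, renamed a 12-month new-detection proportion, keeps the numerator and denominator in step 3. The numerical change is nil in both.

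**The case for a change.** The strongest case for a change is that an MDT diagnosis appears in section 4.1 as an entry condition for the clinic cohort, alongside clinic attendance, and section 3.2.1 does not refer to it. Significant ILD is never defined. If the MDT can diagnose ILD and still call it not significant, two case levels remain after ILA is set aside. With both rounds complete, a written criterion would close off any choice made after seeing the counts, and a sentence costs little.

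Part of this stands. The objective and measure do differ, the link from ILD to MDT diagnosis must be inferred, and the denominators are unstated. The possible gap between a diagnosis and a judgement of significance is the one substantive ambiguity left, and the documents do not show its size. The suggestion of a choice driven by the counts is possible but has no support in the text. The triage took place in care and is described in the past tense, so an analyst would choose between recorded levels rather than judge cases afresh.

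The stronger remedy is no clear improvement. Re-reading baseline scans only for round-2 cases would verify cases and leave non-cases unverified. It would add to prevalence only from people who were rescanned, and it would be done by readers who may know the later result. Without it, disease missed at baseline may be counted as new at round 2. That calls for a caveat when the round-2 figure is reported.

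**Conclusion.** No change to the plan is needed. The extra word in section 3.2.1 is a real inconsistency with section 3.1.1, and the missing criterion and denominators are missing detail in a descriptive primary measure. The natural reading (MDT-diagnosed ILD, round 1 for prevalence, new round-2 diagnoses among those rescanned) gives a sound result. Following it, an analyst would report the numbers offered, scanned and rescanned with exact intervals, which also settles what 1,450 counts.

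The 2.5- to 4.5-fold spread and the 0 to 0.67% range for incidence should not be read as error in the primary result. Both rest on any ILA or fibrotic change standing in for the study's case, which the documents do not support. The conclusion assumes that an MDT diagnosis defines a case and that programme-level counts are available. The clinic data list in section 5 does not mention such counts, but it describes only what clinic participation involves. If the MDT recorded ILD diagnoses that it judged not significant, showing both counts would be enough.

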3.2.2 Secondary Measures

- Symptom burden and duration as per standardised clinical history proformas.
- Quality of life and symptom burden using the following questionnaires:
 - **SF-36**: a widely used validated non-disease-specific questionnaire to assess QoL in multiple diseased populations⁶². The SF-36 is a generic HRQoL instrument, comprising 36 items, grouped into eight domains: physical functioning, role-physical, bodily pain, general health, vitality, social functioning, role emotional, and mental health. Scores are converted into a 100-point scale, higher scores indicating better QoL. The SF-36 has been validated for use in ILD groups including IPF⁶³.
 - **Kings Brief Interstitial Lung Disease (K-BILD)**⁶⁴: developed and validated for specific use in ILD patients. It comprises 3 domains (psychological, breathlessness and activities, chest symptoms and a total score). Scores range from 0-worst to 100-best.
 - The **University of California San Diego Shortness of Breath Questionnaire (UCSD-SBQ)**: a 24-item dyspnea questionnaire that asks respondents to rate themselves from 0 ("Not at all") to

5 ("Maximally or unable to do because of breathlessness") in two areas: 1) how short of breath they are while performing various activities (21 items); and 2) how much shortness of breath, fear of hurting themselves by over exerting, and fear of shortness of breath limit them in their daily lives (3 items). Scores range from 0–120, with higher scores indicating greater dyspnea has demonstrated validity in ILDs trials^{65,66}.

- **Leicester Cough Questionnaire (LCQ)**⁶⁷: is a 19-item questionnaire exploring the impact of cough severity across three domains: physical (eight items), psychological (seven items) and social (four items). The total severity score ranges from 3 to 21, with a lower score indicating greater impairment of health status due to cough. The LCQ has been used as an outcome measure in clinical trial including ILD patients⁶⁸.
- **Fatigue Severity Scale (FSS)**⁶⁹: contains nine items developed to assess disabling fatigue. Item responses are measured on a seven-point Likert type scale ranging from strongly disagree to strongly agree. The nine items are combined into a total score; a lower total score indicates less effect of fatigue on everyday life. The FSS scale has been used in ILD populations⁷⁰.
- **Visual Analogue Scale (VAS)**⁷¹: a single item scale for each symptom - patients are asked to mark cough, breathlessness and fatigue severity on a linear 100 mm visual analogue scale for the past 2 weeks. The extremes of each scale are marked from 'no cough' to 'worst cough'/'no breathlessness' to 'worst breathlessness' and 'no fatigue' to 'worst fatigue'.

- Diagnosis and radiological pattern through clinical MDT proformas
- Full pulmonary function tests
- Shuttle walk tests: distance walked and oxygen saturation (pre and immediately post test)
- Initiated treatments

4 Patient Selection Criteria

4.1 Inclusion criteria

- Age 50-80
- Ever-smokers (current or previous)
- MDT diagnosis of ILD detected through lung cancer screening or through a non-screening pathway
- Attending the regional ILD clinic

4.2 Exclusion criteria

- Unable to complete self-report questionnaire measures e.g. due to cognitive impairment or English not first language

- Unable to provide written informed consent.

Individuals who do not consent to participation in this study will not be disadvantaged in anyway. They will continue to receive ILD clinic assessment, treatment and follow-up as per standard practice.

5 Study Design

4.1 Screening service: Invitation letters, endorsed by GPs to improve participation ^{46,72,73}, were sent to all individuals (n=16, 402), age 55-74, registered at participating GP practices (n=14), asking ever smokers to attend a community-based Lung Health Check (LHC). The LHC, which took place in supermarket carparks in deprived areas of Manchester, assessed symptoms, lung cancer risk (PLCO_{m2012}) and measured spirometry. All participants with a 6-year lung cancer risk >1.5% were offered entry into the screening programme (n=1,450), which involved a non-contrast low dose CT scan at baseline and 12 months later. The first screening round was in 2016 and the second and final screening round in 2017.

4.2 Screening LDCT scans: All LDCT scans (Optima 660, GE Healthcare) use helical acquisition of axial images from lung apices to the costophrenic angles. Imaging is performed without intravenous contrast, in suspended maximal inspiration, with the patient supine and arms above head (scan time 5-10 seconds). Acquisition parameters (kVp and mAs) vary with body weight to achieve a CT dose index below 3.0 millisieverts. Images are reconstructed at 1.25 mm thickness and at 1.25 mm increments. Most CT scans are reported within 2 weeks by practising National Health Service (NHS) Consultant Radiologists with a specific interest in thoracic radiology.

4.3 ILD MDT: Any ILAs detected on screening LDCT scans were highlighted in the CT report and referred to the regional ILD MDT for review and discussion. The MDT consisted of three ILD respiratory physicians, a thoracic radiologist with an interest in ILD, two specialist ILD nurses and an MDT co-ordinator. Once discussed at the MDT, those deemed to have changes suggestive of significant ILD have been referred to the regional ILD service for assessment in the clinic.

4.4 Study population: Individuals attending the regional ILD clinic as a 'new referral' will be invited to participate. Inclusion and exclusion criteria will be evaluated and suitable participants will be provided with a

patient information sheet (PIS) prior to written consent being obtained for enrolment into the study. We will recruit patients from two groups:

- **Group 1:** ILD diagnosed through the Manchester early detection of lung disease pilot (lung cancer screening programme) and
- **Group 2:** age and sex matched individuals with ILD diagnosed through standard non-screening pathway.

Participation at the clinic will involve collection of demographic information, medical history including co-morbidities and medication history, full lung function tests (within 6 weeks), shuttle-walk test (within 6 weeks), MDT outcome proforma, clinic visit outcome including initiation of any treatments and completed questionnaires.

6 Data storage and analysis

Data will be stored on a specially designed research database and analysed using SPSS. The original signed consent form and completed questionnaire are stored within a secured location accessible only to the research team at MFT. Statistical significance will be set at <0.05 . Clinical and demographic data analyses will be descriptive. Questionnaire scores will be calculated according to corresponding scoring algorithms, and mixed-modelling will be used to examine the changes in the various scores between the three time-points, explore factors associated with HRQOL and differences between Group 1 and Group 2.

7 Adverse events

It is not anticipated that any adverse outcomes will occur; direct study participation will only be on the day of clinic visit.

8 Quality assurances

Data entry will be the responsibility of all members of the research team who will check data control as a matter of standard practice.

9 Ethical considerations

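### A questionnaire-completion exclusion covers the whole study, so consenting patients are lost from lung-function, pattern, walk-test and treatment comparisons that need no questionnaire

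*Combined protocol and SAP*

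**What the plan says.** Section 4.2 (Exclusion criteria) has two entries. The first removes anyone "Unable to complete self-report questionnaire measures e.g. due to cognitive impairment or English not first language". The second removes anyone "Unable to provide written informed consent". Neither is limited to particular outcomes.

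The Study population item of section 5 applies the criteria to new referrals at the regional ILD clinic: "Inclusion and exclusion criteria will be evaluated and suitable participants will be provided with a" patient information sheet, and consent follows. Section 5 then lists what participation yields: demographics, history, lung function, shuttle walk, the MDT proforma, the clinic outcome with any treatment started, and the questionnaires. Nothing keeps a patient who cannot do the questionnaires in the study for the rest.

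Section 3.1.2 has four secondary objectives. The first covers quality of life, symptoms and psychological burden. The second is MDT-agreed type and radiological pattern, the third is "Lung function (Forced vital capacity (FVC) and transfer factor (DLCO) at diagnosis", and the fourth is treatment strategy. Section 3.2.2 also lists the shuttle walk as a secondary measure.

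The Screening service item of section 5 dates the first screening round to 2016 and the second, final round to 2017.

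**The concern.** A condition needed for one family of outcomes controls entry to all of them. A patient who can consent, blow into a spirometer, walk the shuttle course and be discussed at the MDT is still left out of every comparison if the forms are beyond them.

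Two things are at stake for objectives 2 to 4 and the walk test.

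- **Precision.** Group 1 comes from a single completed programme, so a case excluded there cannot be replaced by recruiting for longer.
- **Representativeness.** Section 1.3 names participation by hard-to-reach groups as an unresolved issue, and the health checks were placed with access in mind, "which took place in supermarket carparks in deprived areas of Manchester". Selecting on language and cognition narrows the population described, even if both groups lose the same share.

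The wording adds a smaller difficulty. First language describes background, not ability, so recruiters could apply the example differently.

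**Working it through.** The plan states no sample size, expected prevalence or excluded share, so there is no figure to reproduce. The check sets the sections side by side and then illustrates size under stated assumptions.

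**Step 1: which outcomes need a questionnaire** (sections 3.1.2, 3.2.2 and 5)

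| Outcome | Source | Questionnaire needed? |
|---|---|---|
| Objective 1: quality of life, symptoms, psychological burden | Questionnaires, plus clinical history proformas for symptoms and their duration | Largely yes |
| Objective 2: type and pattern | MDT proforma | No |
| Objective 3: FVC and DLCO | Pulmonary function tests | No |
| Objective 4: treatment | Clinic outcome | No |
| Shuttle walk | Test | No |

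**Step 2: whom the criterion removes.** Patients who cannot consent are already out under the second entry. The effect of the first entry alone is the set who can consent but cannot complete the forms. The documents give no size for that set.

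**Step 3: cases available to Group 1.** Inputs:

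- N = 1,450 (Screening service item). The wording attaches this to people offered entry; the number scanned is not given.
- p = 0.9% (diffuse lung disease), 3.8% (other chronic interstitial pneumonia patterns) and 9.7% (interstitial lung abnormalities, which is broader than ILD), from the studies in section 1.4.
- x, the share of cases excluded, is assumed to be 5%, 10% or 20%.

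Cases remaining = N × p × (1 − x). For example, 1,450 × 0.009 = 13.05, and 13.05 × 0.80 = 10.4.

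| p | x = 0 | 5% | 10% | 20% |
|---|---|---|---|---|
| 0.9% | 13.1 | 12.4 | 11.7 | 10.4 |
| 3.8% | 55.1 | 52.3 | 49.6 | 44.1 |
| 9.7% | 140.7 | 133.6 | 126.6 | 112.5 |

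These are illustrations, not forecasts. They ignore clinic non-attendance and refusal.

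**Step 4: precision.** With unchanged variance, the confidence interval for a Group 1 mean widens by 1/√(1 − x):

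- x = 5%: 1/√0.95 = 1.026
- x = 10%: 1/√0.90 = 1.054
- x = 20%: 1/√0.80 = 1.118

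The same factor applies to the difference between groups if each lost Group 1 patient also costs a match in Group 2. If Group 2 kept its full number (1:1 ratio and equal variances assumed; the plan states no ratio), the factor would be √{[1/(1 − x) + 1]/2}. That gives √1.0263 = 1.013 at 5% and √1.125 = 1.061 at 20%.

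**The case against.** The strongest defence is that one cohort with both clinical and questionnaire data is a legitimate choice. Quality of life is the first secondary objective, questionnaires dominate section 3.2.2, and a smaller questionnaire subset could disturb the age and sex matching of Group 2. The matching point stands as a cost but is minor: section 6 already separates descriptive clinical analyses from mixed modelling of questionnaire scores, and balance in the subset can be checked.

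Four further limits stand.

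- **Overlap.** Some patients with cognitive impairment would also fail the consent criterion, so the loss due to this criterion alone is smaller than the number who meet it.
- **Language.** A reader might infer that fluent second-language speakers are barred. The operative test is inability to complete the forms, and first language is only an example of a cause. The wording is loose, but it does not clearly exclude them.
- **Population.** Deprived-area siting says nothing about language or cognition among those screened, and the documents hold no such data.
- **Bias between groups.** A reader might infer that the comparison is biased. The criterion applies to both groups, and nothing shows that it acts at different rates in them.

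**Conclusion.** The point holds for secondary objectives 2 to 4 and the shuttle walk. The plan discards consenting patients from outcomes they could supply, at some cost in precision and representativeness, in a group whose source is closed. The size is unknown. Under an assumed loss of 5% to 20%, Group 1 intervals widen by about 3% to 12%. The effect on the group difference is of that size if matches are lost too, and about 1% to 6% if Group 2 is kept whole at 1:1. At the lowest prevalence in section 1.4, the loss is roughly one to three of 13 cases.

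A reader might go further and infer that the exclusion lowers the primary prevalence estimate. The documents do not support that. Section 3.2.1 sets the measure as "The prevalence and incidence of ILD in participants of a community-based lung cancer screening programme", so its population is the screening programme and not the consented clinic sample. Case finding also comes before the clinic criteria apply: "Any ILAs detected on screening LDCT scans were highlighted in the CT report and referred to the regional ILD MDT for review and discussion". Counted from those records, the effect on prevalence is zero. The plan does not spell out the numerator or its data source, but it nowhere limits the count to enrolled patients.

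This is an eligibility-scope problem that is cheap to correct. It does not threaten the primary result.

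**What to change.** In section 4.2, remove the questionnaire criterion as a study exclusion and make it the definition of the questionnaire analysis set. Reword it as: cannot read and complete the questionnaires in English. Enrol anyone who meets the other criteria and can give written consent for the lung-function, type and pattern, walk-test and treatment outcomes. In section 6, name the two sets and state which outcomes use each. Recording how many new referrals in each group cannot complete the questionnaires would supply the share that the documents lack.

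The cost is an eligibility amendment and two reported denominators. The age and sex balance of Groups 1 and 2 should also be checked within the questionnaire subset, because matching in the full cohort does not guarantee it there.
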